Modeling a similar, successful pilot, we will conduct a pre (control)/post (intervention) study with an anticipated 50 transfer calls in each arm. We will collect pre- and post-intervention data after each eligible transfer call through (1) chart review and access center logs and (2) Qualtrics surveys of referring providers and UW (accepting) providers. We will collect baseline (pre) and post-intervention measures of the potential to avoid transfers, efficiency of transfer communication and execution, provider emotional labor, and patient health outcomes. Providers will utilize the SITe intervention during transfer calls discussing transfer decisions regarding older emergency general surgery (EGS) patients. The research team will be listening retrospectively to recordings of eligible transfer calls through the Calabrio System to observe whether key elements of the intervention items were discussed during the calls. The Calabrio System is a recording system that automatically records transfer calls for the UW Health-Meriter Access Center. Supervisors and managers can access the Calabrio Call Recording Management portal by going to: <https://calabrio.uwhealth.wisc.edu>. We will request access to the Calabrio system and listen to eligible transfer calls directly in the system and will not download any recordings.

Participants:

- Patients: We will include all calls from referring providers requesting transfer of emergency general surgery patients age 60 and older from a referring ED or inpatient floor to the UW ED or inpatient floor.
- Providers: We will include all UW (accepting) surgeons and all referring providers who execute transfer calls of eligible patients. There will be no exclusions regarding referring providers’ position (e.g., physician, mid-level provider), specialty (e.g., emergency medicine, internal medicine), or affiliation (e.g., UW or non-UW).

SITe Intervention Training:

- UW (accepting) surgeons: We will complete SITe intervention training over two months. Utilizing the implementation toolkit developed by stakeholders in Aim 1, we will hold web-based seminars at various dates and times to accommodate differing schedules.

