the electronic medical record to identify eligible patients, UW (accepting) surgeons, and referring providers. We will collect data via review of UW electronic health records and AC logs. Within approximately 48 hours of each qualified transfer, we will email the UW (accepting) provider and referring provider who executed the transfer an approximately three-minute, personalized Qualtrics survey, to be completed at their convenience within an anticipated three days. A survey will be sent during the pre- and post-intervention period. We will also text providers who prefer texting to receive survey links and reminders. We will send reminder emails and/or text to providers who have not responded the surveys before their due date. Since this study is considered a clinical trial, for reporting and grant purposes, we will track provider and patient demographics such as age, gender, and race. We will send accepting providers a pre-survey form requesting their contact information, texting preferences, and request consent to listen to their transfer calls. RPs will be asked to provide demographic information and consent for listening to recordings when taking the actual SITe survey. We have included recording consent language in the surveys. We will listen to eligible transfer call recordings during the pre and post intervention phases to observe if intervention items were discussed during the call. We will listen to call recordings only if both the AP and the RP provide consent to the recording portion of this study. If both providers do not consent to the recording portion, we will review the Access Center notes. No protected health information or patient or provider details will be recorded. The call recordings will stay in the Calabrio system and not be downloaded.

Data analysis:

We will apply descriptive statistics for counts and ordinal measures. We will summarize free text responses regarding AP's perspectives on the following statements:

- "I felt that the reason for transfer was justifiable"
- "I felt that the referring hospital should have been able to care for the patient."
- "I felt respected by the referring provider."

We will also summarize free text responses regarding RP's perspectives on the following statements:

- "I felt that the UW Surgeon doubted whether the transfer was necessary."
- "I felt respected by the UW Surgeon."

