
UW (accepting) surgeons (intervention training):

We will invite all eligible UW (accepting) surgeons to participate by email. We will inform accepting surgeons of the study and provide information about consent. To participate in trainings, providers will provide written consent. Participation will be voluntary. Compensation will be \$100 for the intervention training.

Privacy Plan

All interactions with subjects will take place via email or phone utilizing a UW secure email account and phone line. We will only text providers if they note they prefer their survey links and reminders to be sent via text. We will use a secure UW approved video communication application such as Webex or Zoom to provide trainings to participants. For surveys, we will send a personalized email with the Qualtrics survey link to each provider. We will also ask participants to provide some basic demographic information such as age, race, gender, and years in practice. Subjects will mainly provide responses related to their experience executing an emergency general surgery transfer. Accepting providers will also attend a training via a secure meeting format to learn about the checklist to assist decisions to transfer.

Data Protection Plan

To minimize the risk of a breach of confidentiality, information collected in this study will be kept on a secure server within the UW Department of Surgery network, which is protected by a firewall that ensures the privacy of the network. The data will be stored in a restricted access folder on the department server. Study status tracking will be done in Department of Surgery REDCap, a secure web platform for building and managing online databases and surveys. Access to the information is limited to the study researchers, all of whom will have completed the requisite Collaborative Institutional Training Initiative human subjects and Health Insurance Portability and Accountability Act trainings. The study team will retrospectively listen to eligible transfer calls recordings utilizing the Calabrio system to conduct a retrospective review of the transfer calls to assess whether the information listed in the SITe intervention is discussed. The study calls will not be downloaded or transcribed; they will be listened to in the call recording system. No PHI will be collected from recordings. The research team will simply note the presence or absence of information items in a REDCap form.

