In addition, any field notes will be stored in a locked office in a locked filing cabinet, which will only be accessible to study personnel. For data collection and analysis procedures, all participants will be assigned an identification code. This numeric code, not a name, will be used to label all data collection forms including surveys. After data analysis is complete and the manuscripts have been accepted for publication, hard copies and digital copies of all subject data and records will be destroyed.

Consent Process

The Principal Investigator will send an email to UW (accepting) surgeons and referring providers and CMOs at hospitals that have transferred EGS patients to UW informing them of our study. We have also developed different scripts and flyers to be sent out to accepting providers and referring providers by the UW Health Physician Liaison team, referring hospital CMOs, Wisconsin Surgical Society president, Wisconsin Chapter - American College of Emergency Physicians president, and our current EGS stakeholder group. Our goal is to inform and reach as many referring providers so that we can gather their preferred contact information. We will describe our procedures for administering the Qualtrics survey and provide contact information for questions, feedback, or concerns. After each transfer, we will invite the involved providers to participate in the study by utilizing a recruitment email with a link to complete the survey. At that time, we will obtain electronic consent for each survey. The first page of Qualtrics survey will be the consent page for the survey. The AP's will receive a pre-survey form asking them about their preferred contact information and texting preferences. At the end of this pre-survey form, we will ask their consent to listen to their transfer call recordings. For RPs, we will add consent language for listening to transfer call recordings at the end of the Qualtrics survey. We will only listen to call recordings where both providers consented to listening to calls. If both providers do not consent to the recording portion, we will review the Access Center notes instead. For intervention training, study staff will explain study procedures and obtain consent. Participants will be given a consent form. Participation will be voluntary.

Interviews, Focus Groups, Surveys, Questionnaires

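### Whether SITe items were discussed is checked from the recording or from the Access Center note depending on provider consent, so the source is confounded with referring-provider response and no call is planned to be scored from both

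*Protocol*

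**What the plan says.** Under Study Procedures and Interventions, the team listens to recordings "to observe whether key elements of the intervention items were discussed during the calls". The Data collection text adds that this is done "during the pre and post intervention phases to observe if intervention items were discussed during the call", so the check covers both periods. The Data Protection Plan describes the output: "The research team will simply note the presence or absence of information items in a REDCap form".

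Recordings may be heard only when both providers agree. The Data collection text gives the alternative: "If both providers do not consent to the recording portion, we will review the Access Center notes". The Consent Process section has the same rule with one more word at the end: "If both providers do not consent to the recording portion, we will review the Access Center notes instead".

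The two consents are obtained differently:

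- **Accepting surgeon:** asked on a form separate from the per-call survey. "At the end of this pre-survey form, we will ask their consent to listen to their transfer call recordings".
- **Referring provider:** asked within the survey that follows the call. "RPs will be asked to provide demographic information and consent for listening to recordings when taking the actual SITe survey", and more exactly, "For RPs, we will add consent language for listening to transfer call recordings at the end of the Qualtrics survey".

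The standard operating procedure (SOP) has status codes for providers who cannot be reached (Section 3) and for partial responses and passive declines (Section 4). Section 1, step 4 has staff read the Access Center note of eligible calls for further detail, not for item scoring.

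**The concern.** A recording holds what was said. A note holds what someone wrote down, which may leave out items that were discussed or include items that were not voiced. Falling back to the note is reasonable, since the alternative is no information on those calls. The difficulty is how calls are allocated to the two sources. A call whose referring provider is unreachable, does not respond, stops early or declines goes to the note, and so does a call whose surgeon declined. Recorded calls are those of consenting responders.

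If the two groups then show different item completeness, the data cannot say whether the conversations differed or only the instrument did. If the mix of sources changes between periods, a pooled description could move although the conversations did not. The pilot's pre-post comparison is meant to help understand the measures and design a larger trial. Whether notes can stand in for recordings is something it could usefully learn, and as planned it cannot.

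**Working it through.** **1. Reading the rule.** The fallback sentence could be taken to mean that neither provider consents. The sentence before it allows listening only when both consent, so the coherent reading is: both consent, recording; anything else, note. Item-by-item scoring is spelled out only for recordings. That notes are scored on the same items is inferred from the word saying they are used in place of the recording.

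**2. Why the two sources cannot be separated.** Let m_R and m_N be the true shares of items missing in recorded and in note-only calls, and o the share of discussed items that a note omits.

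- Recorded calls show m_R.
- Note-only calls show m_N + (1 − m_N)·o.
- Difference = (m_N − m_R) + (1 − m_N)·o.

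This is one observed difference with two unknown parts. With m_R = m_N = 10% and o = 10%, note-only calls show 0.10 + 0.90 × 0.10 = 19%, against 10%. With o = 0 and m_N truly 19%, the result is identical. An analysis plan can stratify by source, but it cannot estimate o unless some calls are scored from both.

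**3. Illustrative size.** The protocol gives about 50 calls per period. It gives none of the rates below, so they are assumptions: referring-provider survey completion 30% to 70%, 80% of completers consenting, 90% of surgeons consenting.

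- Share on recordings: 0.3 × 0.8 × 0.9 = 0.216 to 0.7 × 0.8 × 0.9 = 0.504, or about 11 to 25 of 50 calls.
- Share on notes: n = 0.784 to 0.496, or about 39 to 25 of 50 calls.

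If the sources were pooled and m were equal in both groups, the pooled missing share would be m + (1 − m)·n·o:

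| True missing m | o = 5% | o = 10% | o = 20% |
|---|---|---|---|
| 5% | 7.4–8.7% | 9.7–12.4% | 14.4–19.9% |
| 10% | 12.2–13.5% | 14.5–17.1% | 18.9–24.1% |

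The apparent change between periods with no true change is (1 − m)·o·Δn. With m = 10%:

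| Change in share on notes, Δn | o = 5% | o = 10% | o = 20% |
|---|---|---|---|
| 0.10 | 0.5 points | 0.9 points | 1.8 points |
| 0.288 (full range, 0.784 − 0.496) | 1.3 points | 2.6 points | 5.2 points |

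Notes that contain unvoiced items would push the other way, so the direction is not settled either.

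**The case against.** The strongest case against is that nothing here is wrong as written. The fallback is sensible, no section says the sources will be pooled, and the source should be identifiable for each call, so results can be split later. Reporting by source is ordinary analysis-plan content. This largely stands. What remains is the data-collection rule: the protocol decides which source is read for which call, and without dual scoring agreement cannot be estimated afterwards.

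Three stronger readings are tempting and not supported:

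- **The fidelity criterion is compromised.** The opening summary defines fidelity as less than 15% missing patient information but names no source. It could mean blanks on the tool itself, and nothing makes it a go/no-go rule.
- **The pre-post comparison is biased.** Item completeness is not among the pre-post measures listed under Study Procedures and Interventions, and formal efficacy tests are ruled out. That response will differ between periods is conjecture. Referring providers get a further letter and email at the start of training, and the contact list grows. But they are also written to at the start of the study, and the SOP calls for an external search even where contact details came from liaisons or past searches.
- **Notes should become the single instrument.** Under the omission model, notes alone carry the largest error: with m = 5%, they show 0.05 + 0.95 × 0.10 = 14.5% at 10% omission and 0.05 + 0.95 × 0.20 = 24.0% at 20%. Access Center nurses are also part of the intervention's structure, so what they write could itself change after implementation.

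**Conclusion.** The concern holds in a limited form. The source of the item check is confounded with referring-provider response, and no call is planned to be scored from both sources. For the surgeon, the dependence is by surgeon more than by call. Nothing rules dual scoring out; it is simply not planned.

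The size and direction of any distortion are unknown. The figures above rest wholly on assumed response, consent and omission rates, and they matter only if the sources are combined. Because the pilot is descriptive and no stated criterion is tied to this review, the point is minor: a cheap improvement and not a flaw that threatens the study's conclusions.

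**What to change.** 1. In both periods, score the Access Center note on the same REDCap item form for every eligible call, including those whose recording is scored. Staff already read the note at screening.
2. Keep scoring the recording wherever both providers consent. It remains the better measure of what was said; the note should not be treated as the reference.
3. Use the dual-source calls to estimate agreement between note and recording, separately by period.
4. Report item completeness by source, with the number of calls in each period, and do not pool the sources unadjusted.
5. If the 15% fidelity figure is to be read from this review, name its source in advance. If fidelity means blanks on the tool, keep this review as a separate description.

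**Cost.** A few minutes of abstraction per call and a wording change. Source-specific figures are less precise. Assume 10 items per call, within-call correlation 0.1 and 10% missing, so the design effect is 1 + 9 × 0.1 = 1.9. The 95% half-width, 1.96·√(0.1 × 0.9 × 1.9 / (10k)), is then 3.6 points for k = 50 calls, 5.1 for 25 and 7.7 for 11. For a 20% omission rate over 9 discussed items per call, the design effect is 1 + 8 × 0.1 = 1.8. The half-width, 1.96·√(0.2 × 0.8 × 1.8 / (9k)), is 7.0 points with 25 dual-source calls and 10.6 with 11. Over both periods it is 5.0 points (50 calls) to 7.5 points (22 calls).

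Agreement would be estimated only among consenting responders. Applying it to the other calls means assuming that notes omit items at the same rate there, and that should be stated.

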Appendix

- Appendicitis – infection of the appendix

Blockages of the intestine

- Obstruction
 - Common causes: adhesions (scar tissue) from previous surgery, hernias, cancer
 - **Notes in Qlikview/healthlink may refer to SBO, small bowel obstruction**
- Volvulus (twisting)
 - Gastric (stomach)
 - Cecal (first part of the colon)
 - Sigmoid (second to last part of the colon)

[figure not shown]
Perforated viscus (hole in the intestine)

- Ulcer
 - Gastric (stomach)
 - Duodenal (first part of small intestine)
 - Parts of the colon
 - Gastrojejunal (patient has had previous surgery [often gastric bypass] so now stomach (gastro) is sewn to small bowel (jejunum))
- Obstruction (blockage)
- Tumor
 - GIST (gastrointestinal stromal tumor)
 - Cancers

Enteritis (infection or death of the intestines) or colitis (of the colon)

- Inflammatory bowel disease
 - Crohn's disease – can occur throughout any part of the intestine; often causes strictures or fistulas
 - Ulcerative colitis – always starts at the rectum (last part of the large intestine and then moves up)
- Ischemic (dead or not enough blood supply)
 - Vascular blockage or insufficiency (celiac artery, SMA [superior mesenteric artery], IMA [inferior mesenteric artery])
 - Low flow state due to patient being hypotensive (blood pressure low)
- Infectious
 - C. diff (Clostridium difficile) – if severe can be called toxic megacolon

Anal fistula

Diverticulitis

- - Typically of the colon
 - Can be limited to the colon itself or there can be an associated abscess or a “free” perforation (if contained, limited to the area around the colon; if “free” perforation, there is lots of air and gas outside the colon and often surgery is needed)
 - Meckel's diverticulitis – diverticulum (outpouching) of the small intestine that can become infected and/or perforate

Anorectal problems

- Abscess
- Anal fissure – tear in the tissue that lines the anus
- Fistula

Pancreatitis (inflammation of the pancreas that may or may not become infected)

- Common causes: alcohol, gallstones, medications
- Depending on how the pancreas heals, it can go on to develop the following:
 - Pancreatic necrosis – part of the pancreas dies
 - Pancreatic pseudocyst – it heals such that a fluid filled cyst replaces part of the pancreas; depending on where it is and how big sometimes it can cause obstructions of the stomach (gastric outlet obstruction) or intestine

Compartment syndrome

- Extremity
 - When there is so much pressure built up in the extremities (usually the leg but sometimes the butt), that the muscle has nowhere to go and could die
 - Treatment is fasciotomy (open the fascia surrounding the muscle)
- Abdominal
 - When there is so much pressure built up in the abdomen (often due to pancreatitis or dead gut), that patients become horribly ill because blood cannot return to the abdomen and there is so much pressure that they often cannot expand their lungs fully
 - Treatment is exploratory laparotomy (open the belly)

Supplemental File 2: Aim2GEMSSTAR_EmailScript_InvitationToSurvey_PrelInt 12.14.23 No PHI

Subject: Tell us about your recent transfer call – Respond by **[DATE]** - SITe research study

Dear **[insert provider name]**,

In the last 48 hours, you were involved in a call through the UW Health-Meriter Access Center about transferring an older (≥ 60 year old) emergency general surgery (EGS) patient. We invite you to participate in a study to **Support Interhospital Transfer Decisions (SITe)**, which focuses on communication about transfers for older EGS patients.

Participation involves taking a **3-minute online survey** about your experience communicating with the other provider during the call. Your information and responses will be kept confidential.

Below is a brief summary of the call:

- RP summary: A [age] year old [sex] with a diagnosis of [diagnosis] was discussed with Dr. [AP Last name]. The transfer [was/is] [accepted/denied/pending].
- AP summary: Dr. [RP last name] requested transfer for a [age] year old [sex] with a diagnosis of [diagnosis]. You [accepted/denied] the transfer.

To participate, please click <https://go.wisc.edu/site> and enter **[unique ID]** in the first question. Please complete the survey by **[DATE]**.

Please note that we might ask you to complete the same survey about other transfers in the future. This study is led by [name] at the University of Wisconsin-Madison and is funded by the National Institute on Aging.

We are sincerely grateful for your time since your role is critical in the transfer process. Please contact [contact] with any questions.

Supplemental File 3: Aim2GEMSSTAR_SITe survey reminder email_preint

Mark as high priority

Subject: **Reminder:** Tell us about your recent transfer call – Respond by **[DATE]** – SITe Research Study

Dear **[Provider name]**,

This is a friendly reminder to complete the SITe survey **by midnight tomorrow [DATE]**. To participate, please click <https://go.wisc.edu/site> and enter **[unique ID]** in the first question.

This 3-minute survey asks about your experience communicating with the **[UW accepting surgeon/referring provider]** in a recent transfer call. For your reference, here is a summary of the recent transfer call:

[insert summary from original email]

Thank you for your time and support of this important initiative.

Respectfully yours,

[Your name]

[Insert study email signature]
